9.3.2 Notification of the Sponsor of Serious Adverse Events

Any AE that meets a protocol-defined serious criterion must be submitted on an SAE form to the DMID CROMS Pharmacovigilance Group (PVG), the DMID Pharmacovigilance contractor **immediately** (within 24 hours of site awareness), at the following address:

DMID CROMS Pharmacovigilance Group (PVG) Technical Resources International, Inc [name] Bethesda, MD 20817 USA Email: XXXXXXXXX Fax: XXXXXXXXX SAE line: XXXXXXXXX

Other supporting documentation of the event may be requested by the DMID Pharmacovigilance contractor and should be provided as soon as possible.

The DMID Medical Monitor (MM) and Clinical Project Manager (CPM) will be notified of the SAE. The DMID MM will review and assess the SAE for regulatory reporting and potential impact on study subject safety and protocol conduct.

Questions about SAE reporting can be referred to the SAE line (available 24 hours a day/7 days a week).

9.3.3 Regulatory Reporting for Studies Conducted Under DMID-Sponsored IND

Following notification from the investigator, DMID, the IND sponsor, will report any suspected adverse reaction that is both serious and unexpected. DMID will report an adverse event as a suspected adverse reaction only if there is evidence to suggest a causal relationship between the drug and the adverse event. DMID will notify FDA and all participating investigators (i.e., all investigators to whom the sponsor is providing drug under its INDs or under any investigator's IND) in an IND safety report of potential serious risks from clinical trials or any other source, as soon as possible, but in no case later than 15 calendar days after the sponsor determines that the information qualifies

for reporting as specified in 21 CFR Part 312.32. DMID will also notify FDA of any unexpected fatal or life-threatening suspected adverse reaction as soon as possible but in no case later than 7 calendar days after the sponsor's initial receipt of the information. Relevant follow-up information to an IND safety report will be submitted as soon as the information is available. Upon request from FDA, DMID will submit to FDA any additional data or information that the agency deems necessary, as soon as possible, but in no case later than 15 calendar days after receiving the request.

All serious events designated as "not related" to study product(s), will be reported to the FDA at least annually in a summary format.

9.3.4 Reporting of Pregnancy

Although not AEs, pregnancies are reportable events. Any pregnancies that occur during the study period in women who have received any study product will be reported via the Emmes Internet Data Entry System (IDES) on the Pregnancy Report form within 5 days of site awareness. The report will include pregnancy outcome (e.g., any premature terminations, elective or therapeutic, and any spontaneous abortions or stillbirths), as well as the health status of the mother and child, including date of delivery and infant's gender and weight. Pregnancies will be followed until birth. All pregnancies will be reported to the clinical data management group. If the database is locked at time of pregnancy, a supplemental report will be generated and completed after birth and 3 month follow up, which will be appended to the database.

9.4 Investigator's Assessment of Adverse Events

The determination of seriousness, severity, and causality will be made by an onsite investigator who is qualified (licensed in the state) to diagnose adverse event information, provide a medical evaluation of adverse events, and classify adverse events based upon medical judgment. This includes but is not limited to physicians, physician assistants, and nurse practitioners. Laboratory abnormalities will be reported as AEs based on the normal range of values for the laboratory. The grading of the laboratory AEs will be based on the DMID toxicity table (Appendix B).

9.4.1 Assessment of Seriousness

Event seriousness will be determined according to the protocol definition of an SAE (Section 9.2).

9.4.2 Assessment of Severity

Event severity will be graded according to parameters shown in Appendix B or if not, noted in the tables using the definitions below:

- 1 = Mild (awareness of a symptom but the symptom is easily tolerated; the symptom requires minimal or no treatment)
- 2 = Moderate (discomfort enough to cause interference with usual activity)
- 3 = Severe (incapacitating; unable to perform usual activities; requires absenteeism/bed rest)
- 4 = Life-threatening
- 5 = Death

9.4.3 Assessment of Association

Relationship to Study Products: The clinician's assessment of an AE's relationship to test article (vaccine or study drug) is part of the documentation process, but it is not a factor in determining what is or is not reported in the study. If there is any doubt as to whether a clinical observation is an AE, the event should be reported. All AEs must have their relationship to study product assessed using the terms: related or not related. In a clinical trial, the study product must always be suspect. To help assess, the following guidelines are used.

Related – There is a reasonable possibility that the study product caused the adverse event. Reasonable possibility means that there is evidence to suggest a causal relationship between the study product and the adverse event.

Not Related – There is **not** a reasonable possibility that the administration of the study product caused the event.

9.4.4 Assessment of Reactogenicity

Subjects will be asked to record events daily on an 8-day subject memory aid. The subject will record temperature and the presence and intensity of post-vaccination reactogenicity events, including pain, tenderness, erythema, induration and warmth at the at injection site; fever, chills, arthralgia/joint pain, malaise/fatigue, myalgia/body aches, headache, nausea, vomiting, abdominal pain and any other symptoms they might be experiencing after vaccination. Erythema and induration at the vaccination site will be measured in millimeters. Any symptoms still present at Day 8 will continue to be followed until symptom resolution. Subjects will also be asked to record any medications taken and any emergency room or physician visits (other than routine check-ups). The subject memory aid will be reviewed with the subject at subsequent clinic visits and phone calls as needed.

Symptoms will be graded using the following scale:

- Grade 0: Not present
- Grade 1: Mild (present but easily tolerated)

- Grade 2: Moderate (able to tolerate routine activity with effort)
- Grade 3: Severe (unable to continue routine activity)

This information will be reviewed by study staff during follow-up subject contacts.

In the event a subject experiences an adverse event or injection site reaction that is still present at the end of the subject's participation in the study, the subject must be followed until resolution or until the event or abnormality resolves to the investigator's and/or sponsor's satisfaction. Follow-up procedures, evaluations, and outcomes will be recorded on the subject's data collection forms.

9.5 Safety Monitoring by the DMID Safety Oversight Mechanism

9.5.1 Data Safety and Monitoring Board (DSMB)

Safety oversight will be under the direction of a DSMB. The DSMB will meet at least annually (to be determined by the DSMB) to assess safety and enrollment data in addition to the planned interim analysis. If halting rules are initiated or the DSMB requests additional meetings, more frequent meetings may be held. The DSMB will operate under the rules of a DMID-approved charter that will be written at the organizational meeting of the DSMB. The DSMB will advise DMID of its findings. The DSMB will review blinded aggregate safety data for increased rate of occurrence of serious suspected adverse reactions

9.5.2 Independent Safety Monitor (ISM)

Safety oversight for this study will include an ISM in close proximity to each of the clinical research sites. The ISM will receive and evaluate SAEs blinded and provide an independent written summary to the DMID Clinical Project Manager and DMID Medical Monitor. The ISM may be asked by the DMID Medical Monitor to review additional safety events (i.e. significantly increased frequency of non-serious adverse events).

9.5.3 Interruption or Discontinuation of Study Enrollment and Study Product Administration for all Subjects in the Study

DMID, as the study sponsor, may interrupt study dosing and/or study entry at any time if medically indicated. To minimize risk, cumulative safety data will be reviewed by the Data and Safety Monitoring Board (DSMB), as expeditiously as is reasonable. The DSMB may recommend terminating the study if deemed necessary following a vaccine-related SAE.

9.6 Halting Criteria/Rules

If the trial is halted, study drug will not be administered to any additional subjects, and enrollment will stop until the DSMB has reviewed the event.

After their review, the DSMB will make a recommendation to DMID whether the study should continue per protocol, proceed with caution, be further investigated, be discontinued, or be modified and then proceed. Suspension of enrollment (for a particular group or for the entire study) is another potential outcome of a safety review.

Subsequent review of serious, unexpected, and related AEs by the medical monitor, DSMB, IRB, the Sponsor, the FDA, or relevant local regulatory authorities may also result in suspension of further trial interventions/administration of study product at a site. The FDA and study Sponsor retain the authority to suspend additional enrollment and study interventions/administration of study product for the entire study, as applicable. The following events will trigger a safety review:

- If two subjects experience a systemic adverse event that is judged to be severe (Grade 3) and related to vaccination. Number of events contributing to halting rule is the sum of a and b:
 - a. Solicited severe (Grade 3) systemic reaction that is judged to be related to the vaccination. Solicited reactions are assumed to be associated with vaccination.
 - b. Severe (Grade 3) adverse event that is judged to be related to the vaccination.
- If 1 subject experiences an SAE judged by an investigator to be related to vaccination.
- If 1 subject develops a laboratory value that is considered Severe (Grade 3) and that is judged to be related to vaccination. Includes all lab values that are considered severe. Relatedness must be determined by the medical monitor.

10 Clinical Monitoring

10.1 Site Monitoring Plan

Clinical monitoring at the site will be conducted to verify that the study is conducted according to the approved protocol, human subjects are protected, and data collection processes are of high quality and meet sponsor SOPs, GCP/ICH guidelines, and federal regulations. DMID, the sponsoring agency, or its designee will conduct site monitoring visits as detailed in the monitoring plan or in the Manual of Procedures (MOP).

Site visits will be made at standard intervals or more frequently as defined by DMID. Monitoring visits will include, but are not limited to, review of regulatory files, study product accountability records, data collection forms, case report forms, informed consent forms, medical and laboratory reports, and protocol compliance. Study monitors will meet with investigators to discuss any problems and actions to be taken and document visit findings and discussions. Clinical monitoring reports will be submitted to DMID.

11 Statistical Considerations

11.1 Study Hypotheses

The primary objective of the trial is to assess the safety and evaluate the efficacy of new candidate hepatitis C virus vaccines, AdCh3NSmut1 and MVA-NSmut, compared to placebo when administered sequentially to IDU. This Phase I/II study is intended primarily to uncover any safety issues that occur at a sufficiently high rate that they might be observed in a study of this size, and to obtain meaningful estimates of the efficacy of the vaccine against chronic HCV infection. While the limited sample precludes reaching definitive conclusions, descriptive analyses will be supplemented by hypothesis testing and estimation of vaccination effects when feasible. For the primary safety and efficacy endpoints, the null hypothesis of no difference in vaccine versus placebo arms will be tested against a two-sided alternative at the p = 0.05 level.

11.2 Sample Size Considerations

Sample size calculations are based on the assumption of detecting a 60% reduction in incidence of chronic infection over 18 months of post-vaccination follow-up among vaccinated subjects compared to unvaccinated controls in an according to protocol (ATP) analysis. A total of 43 observed events of chronic infection in the ATP cohort would provide power of 85% for a two-sided log rank test conducted at the significance level (alpha) of 0.05 to detect a 60% reduction in hazard rate. The incidence of chronic infection among controls is assumed to be 14% annually.³⁰ Assuming 14 cases/100 person-years (PY) in the control arm, and 5.6 cases/100 PY in the vaccine arm, a total of 292.5 subjects in the ATP cohort followed for 1.5 years would provide on average 43 events. We further assume that 65% of enrolled subjects will be retained in the ATP cohort. Therefore, we inflate the required number of subjects by a factor of 1/0.65 and obtain a target enrollment of 540 subjects, or 270 subjects per vaccination arm.

As described in Section 11.3, the DSMB will conduct a blinded examination of progress towards the goal of 43 observed events of chronic infection in the ATP cohort, and decide whether to recommend an extension of the enrollment period. At the September 2, 2015 DSMB meeting, the DSMB reviewed the progress towards this goal and recommended increasing the target enrollment from 450 to 540 subjects, or 270 subjects per vaccination arm.

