11.4.5 Evaluation of Exploratory Efficacy Endpoints

1. Reduction in incidence of primary HCV infection associated with AdCh3NSmut1 and MVA-NSmut HCV vaccines

HCV RNA and and/or anti-HCV will be used to classify incident infection, using the definition described in Section 3.3 (page 20). The observed cumulative incidence of primary HCV infection in the IDU populations participating to the study has been observed at 27%/100 PYO³⁰. Analyses will be performed in both ATP and mITT populations. The analyses will be based on comparisons of incidence of HCV infection between study groups using a log-rank test for time to midpoint in both ATP and mITT populations. A sensitivity analysis will also be performed using interval censoring methods.

2. Reduction of HCV chronic infection with a 9 month chronic cut-off associated with AdCh3NSmut1 and MVA-NSmut HCV vaccines

Previous data have shown that acute HCV infection in individuals followed for two years is cleared in 86% of cases by 6 months, but in a small number, clearance occurs after 6 months (95% at 12 months³⁰). We will assess the reduction in incidence of chronic infection based on 9 months follow up after incident infection. HCV RNA assays will be used to classify chronic infections at 9 months using the definition described in Section 3.3 (page 20). Analysis will be performed in both ATP and mITT populations.

3. Reduction of peak concentration (magnitude) of HCV RNA associated with AdCh3NSmut1 and MVA-NSmut HCV vaccines

Quantitative measures of HCV RNA concentration will be compared between vaccinated and controls. We expect to observe a reduction of 3 log values of the maximum concentration of RNA detected in the blood in vaccinated subjects who develop HCV viremia (similar to that observed in subjects with HCV reinfection²⁹), compared to the placebo group. Quantitative viremia measures, including the initial peak and total HCV RNA levels (described in Section 3.3 page 20) be compared, between vaccinated and placebo arms, using logarithmic IU/mL values, by Kruskal-Wallis test, and a non-parametric equality of median tests. Analysis will performed in both on ATP, and mITT populations.

4. Reduction in the duration of HCV viremia following incidence HCV infection associated with AdCh3NSmut and MVA-NSmut HCV vaccines

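### The stated yield of 43 events from 292.5 ATP subjects ignores removal from the risk set after an event; at the stated rates it is about 39.5, though the 540-subject target still meets the goal

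*Protocol*

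**What the plan says.** Protocol 11.2 sets the event goal first: "A total of 43 observed events of chronic infection in the ATP cohort would provide power of 85" percent, "for a two-sided log rank test" "conducted at the significance level (alpha) of 0.05", "to detect a 60% reduction in hazard rate". It then turns events into subjects. The control rate is introduced with "The incidence of chronic infection among controls is assumed to be 14% annually", and the next sentence restates it as a rate in each arm: "Assuming 14 cases/100 person-years (PY) in the control arm, and 5.6 cases/100 PY in the vaccine arm". On those rates, "a total of 292.5 subjects in the ATP cohort followed for 1.5 years would provide on average 43 events". SAP 5 carries the same calculation.

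The paragraph goes on to assume 65% retention in the ATP cohort and gives a target enrolment of 540, or 270 per arm. Both documents attribute the rise from 450 to 540 to the DSMB review of September 2015.

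The primary endpoint (Protocol 3.1.2) is chronic infection six months after a first detected infection. Protocol 11.4.3 and SAP 8.1 analyse it as time to event. An infected subject is either an event or is censored at the sample nearest six months after infection. Under Protocol 8.3, infected subjects leave the study about 270 days after detection.

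**The concern.** Multiplying a rate by planned follow-up gives the right count only if everyone stays at risk for the whole period. Here a subject who becomes chronically infected at month 6 cannot have a second event at month 15, yet the product still counts that remaining time. At a control rate of 14 per 100 person-years over 1.5 years, nearly one control in five is expected to have the event, so the lost time is not negligible.

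The 292.5-subject sentence is the only place where either document converts subjects into events. If the conversion is too favourable, the stated 85% power is attached to a cohort too small to deliver it. Anyone applying the same product to a different cohort size would carry the error forward.

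**Working it through.** **Inputs** (Protocol 11.2 and SAP 5, except allocation): two-sided alpha 0.05; power 85%; hazard ratio 0.40; rates 0.14 and 0.056 per person-year; follow-up 1.5 years; 65% ATP retention; 1:1 allocation (Protocol section 4).

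**1. The event goal.** Schoenfeld's formula for equal arms is d = 4(1.960 + 1.036)² / (ln 0.4)² = 42.8, so 43 events. Power is Φ(√d × |ln 0.4|/2 − 1.96); at d = 43 this is 85.2%. The goal is reproduced and is correct.

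**2. The plan's event yield.** 292.5 × 1.5 = 438.75 person-years. The average rate is (0.14 + 0.056)/2 = 0.098. The product is 438.75 × 0.098 = 43.0, which matches the stated figure and shows that every subject is credited with a full 1.5 years at risk.

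**3. The yield with at most one event per subject.** With constant hazards, expected events = N/2 × [(1 − exp(−0.14 × 1.5)) + (1 − exp(−0.056 × 1.5))]. The two risks are 1 − exp(−0.21) = 0.1894 and 1 − exp(−0.084) = 0.0806. For N = 292.5:

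- control: 146.25 × 0.1894 = 27.7
- vaccine: 146.25 × 0.0806 = 11.8
- total: 39.5 events, from 408.3 rather than 438.75 person-years at risk
- power at 39.5 events: 82.1%

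**4. ATP subjects needed for 43 events.** The average risk is (0.1894 + 0.0806)/2 = 0.135, and 43/0.135 = 318.5, so about 319 ATP subjects, or about 490 enrolled at 65%.

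**5. The current target.** 540 × 0.65 = 351 ATP subjects.

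| ATP subjects | Method | Events | Power |
|---|---|---|---|
| 292.5 | rate × full person-time (as stated) | 43.0 | 85.2% |
| 292.5 | constant hazards, one event each | 39.5 | 82.1% |
| 351 | rate × full person-time | 51.6 | 90.8% |
| 351 | constant hazards, one event each | 47.4 | 88.4% |

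**6. Sensitivity: first infection ends time at risk.** This assumes that first infections occur at 27 per 100 person-years, the figure in Protocol 11.4.5 ("in the IDU populations participating to the study has been observed at 27%/100 PYO"), and that 14 per 100 is the chronic-infection rate before first infection. With 1 − exp(−0.27 × 1.5) = 0.333 and 351 ATP subjects:

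- infection rate equal in both arms: 175.5 × 0.333 × (0.14 + 0.056)/0.27 = 42.4 events, 84.7% power
- vaccine also cuts infection by 60%: 43.9 events, 85.9% power

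**The case against.** Four points can be made for the plan.

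First, the design now enrols 540. A reader might infer from step 3 that the trial yields only 39.5 events and is underpowered. The documents do not support that. The 292.5 figure is 65% of 450, the target that preceded 540 (292.5/0.65 = 450). At 540 the corrected expectation exceeds the goal. This objection stands in full.

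Second, power is tied to observed events, and the DSMB reviewed blinded progress towards 43. SAP 14 records its recommendation that 85% power be maintained and enrolment continue to 540. That also stands, and it limits the practical harm. It does not make the conversion sentence correct.

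Third, if 14% annually is read as a one-year risk, the exponential model gives 42.3 events (hazard ratio 0.4) or 41.7 (14% and 5.6% both as risks), close to 43. But the sentence containing the calculation states rates per 100 person-years, and the person-year product gives 43.0 exactly.

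Fourth, a reader might go further and combine first-infection exit at 27 per 100 with 292.5 subjects. That gives 35.4 to 36.6 events, 78% to 79% power, and, at the lower count, a need for about 356 ATP subjects. The documents do not establish these figures. Pairing 14 with 27 implies that 52% of infections become chronic (14/27), whereas Protocol 2.1 puts it at 70–80%. Using 27 per 100 with that chronicity, a 60% reduction and equal infection rates gives 146.25 × 0.333 × (0.70 to 0.80) × 1.4, about 48 to 55 events. The infection rate can therefore move the count either way, depending on a link that the documents do not state.

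**Conclusion.** The stated yield is wrong as written, and the point is minor. At the plan's own rates, 292.5 ATP subjects give about 39.5 events, 8% fewer than stated, and about 3 percentage points less power. The cohort that delivers 43 events is about 319. This rests on constant hazards, equal arms, 1.5 years of follow-up for subjects without an event, and Schoenfeld's approximation, which is the one that reproduces the plan's 43.

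It is not a finding that the trial is too small. At 351 ATP subjects the expectation is about 47 events and 88% power if 65% retention holds. The first-infection scenario gives about 42 to 44 events and 85% to 86% power, essentially at goal, and is conditional on the assumptions in step 6.

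**What to change.** In Protocol 11.2 and SAP 5, replace the 292.5-subject sentence with expected events computed as N/2 × [(1 − exp(−0.14 × 1.5)) + (1 − exp(−0.056 × 1.5))]. State that 43 events need about 319 ATP subjects, and that 351 ATP subjects (65% of 540) are expected to give about 47 events and 88% power. Writing the paragraph for 351 also removes the mismatch by which 292.5/0.65 is said to give 540 when it gives 450.

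If exit at first infection is shown, label it as a sensitivity scenario, with both assumptions stated and the range of 42 to 44 events.

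The cost is a few sentences in each document, and the figure for 292.5 subjects becomes less favourable. Enrolment, the 43-event goal and the analysis are unchanged.

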11.3 Planned Interim Analyses

The DSMB will meet and review safety data and enrollment data at least annually as outlined in the DSMB charter. The study will be monitored to determine if any of the

safety halting rules described above in Section 9.6 are met. Additionally, there will be two planned interim analyses.

The first interim analysis is planned when study Day 63 (approximately week 9) followup data is available on the last of approximately 68 subjects enrolled in Stage 1 of the trial. The second interim analysis is planned to occur when roughly one-third of enrolled and currently per-protocol subjects (N = 98) have completed six months of postvaccination follow-up, but no later than one month prior to the planned completion of enrollment to the trial. Both the first and second interim analysis will be fully blinded and will report on trial data aggregated across both treatment arms.

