5. SAMPLE SIZE CONSIDERATIONS

Sample size calculations are based on the assumption of detecting a 60% reduction in incidence of chronic infection over 18 months of post-vaccination follow-up among vaccinated subjects compared to unvaccinated controls in an according to protocol (ATP) analysis. A total of 43 observed events of chronic infection in the ATP cohort would provide power of 85% for a two-sided log rank test conducted at the significance level (alpha) of 0.05 to detect a 60% reduction in hazard rate. The incidence of chronic infection among controls is assumed to be 14% annually [10]. Assuming 14 cases/100 person-years (PY) in the control group, and 5.6 cases/100 PY in the vaccine group, a total of 292.5 subjects in the ATP cohort followed for 1.5 years would provide on average 43 events. We further assume that 65% of enrolled subjects will be retained in the ATP cohort. Therefore, we inflate the required number of subjects by a factor of $1/0.65$ and obtain a target enrollment of 540 subjects, or 270 subjects per vaccination group.

The original enrollment target of the study was 344 subjects. At the April 29, 2014 DSMB meeting, the DSMB reviewed the progress towards the goal of 43 observed events of chronic infection in the ATP cohort and recommended increasing the target enrollment from 344 to 450, or 225 subjects per vaccination group.

At the September 2, 2015 DSMB meeting, the DSMB reviewed the progress towards the goal of 43 observed events of chronic infection in the ATP cohort and recommended increasing the target enrollment from 450 to 540 subjects, or 270 subjects per vaccination group.

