14. SUMMARY OF CHANGES IN THE CONDUCT OF THE STUDY OR PLANNED ANALYSES

The DSMB met on April 29, 2014 for a Data Review Meeting for a routine safety review. The DSMB recommended the sample size be increased to 450 subjects to replace dropout subjects. The protocol was amended on October 29, 2014 to version 7.0 to increase enrollment from 344±8 to 450±8 and extended the study duration from 47 to 54 months.

The DSMB met on September 2, 2015 for a Data Review Meeting and to review aggregate endpoint and enrollment data. The objective of this meeting was to conduct a blinded examination of progress towards the statistical information goal and to decide whether to recommend an extension of the enrollment period. The DSMB identified no safety concerns and recommended that the study continue as per the protocol. They also recommended that an 85 percent power with a two sided confidence interval was maintained and that enrollment should continue until 540 subjects are enrolled. The protocol was amended on October 6, 2015 to Version 9.0 to increase enrollment from 450±8 to 540±8 and extended enrollment from 54 to 63 months.

The definition of incident HCV infection for exploratory endpoint 1 in this SAP differs slightly from the definition in the protocol. In this SAP, two definitions of incident HCV infection are used: one which incorporates HCV RNA results only, and one that utilizes the anti-HCV testing results (see Section 3.3.3).

A number of exploratory analyses of the efficacy, immunogenicity, and risk behavior data were added to supplement the outcome measures defined in the protocol.

The protocol uses the terms “primary infection”, “acute infection”, and “incident infection” to describe the incident infection of HCV. This SAP replaces these terms with “incident infection”.

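### The printed sample-size derivation does not give 540: 292.5 / 0.65 = 450, and at 540 the stated inputs imply about 52 events and 91% power

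*Protocol*

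**What the plan says.** Protocol 11.2 builds the sample size in four steps, and SAP 5 repeats them.

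- **Events.** "A total of 43 observed events of chronic infection in the ATP cohort would provide power of 85" per cent, for a "two-sided log rank test conducted at the significance level (alpha) of 0.05 to detect a 60% reduction in hazard rate".
- **ATP subjects.** With 14 chronic infections per 100 person-years on control and 5.6 on vaccine, 292.5 ATP subjects followed for 1.5 years are expected to yield 43 events.
- **Retention.** "We further assume that 65% of enrolled subjects will be retained in the ATP cohort" (SAP 5; the protocol has the same assumption).
- **Enrollment.** From this, "we inflate the required number of subjects by a factor of 1/0.65 and obtain a target enrollment of 540 subjects". The SAP ends the same way: "and obtain a target enrollment of 540 subjects, or 270 subjects per vaccination group".

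The next paragraph of Protocol 11.2 gives a different origin for the figure. On 2 September 2015 the DSMB reviewed progress towards 43 events and "recommended increasing the target enrollment from 450 to 540 subjects, or 270 subjects per vaccination arm". SAP 5 adds that the target was 344 at the start and 450 from April 2014. SAP 14 records the 2015 recommendation as being that "an 85 percent power with a two sided confidence interval was maintained and that enrollment should continue until 540 subjects are enrolled".

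**The concern.** The enrollment sentence presents 540 as the output of a calculation whose inputs are printed just before it, and those inputs give 450, the target that was in force before the 2015 increase. It looks as though the end figure was replaced while the 65% retention and the 14 per 100 person-years were left alone.

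What is at stake is the planning statement, not the trial's power. The 85% is tied to 43 observed events, whatever the enrollment. But a reader who follows the chain concludes that 540 enrolled was expected to yield 43 events and 85% power, and the printed assumptions do not say that. Two quite different situations fit the text: 540 is a margin above unchanged assumptions, or it compensates for retention or incidence lower than printed. The distinction matters when a null result, or a final count near 43, has to be interpreted in the study report.

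**Working it through.** **Inputs** (Protocol 11.2 and SAP 5): hazard ratio 0.4; two-sided alpha 0.05; power 85%; rates 0.14 and 0.056 per person-year; 1.5 years of follow-up; 65% retention. Allocation is 1:1 (Protocol 4).

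**1. Events: reproduced.** Schoenfeld's formula for 1:1 allocation is D = 4(z₀.₉₇₅ + z₀.₈₅)² / (ln HR)². With z values of 1.960 and 1.036 and ln 0.4 = −0.916, D = 42.8, which rounds up to 43. Power at 43 events is Φ(√43 × 0.916/2 − 1.960) = 85.2%.

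**2. ATP subjects: reproduced.** The mean rate is (0.14 + 0.056)/2 = 0.098 per person-year. Then 292.5 × 1.5 × 0.098 = 43.0 events.

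**3. Inflation: not reproduced.** 292.5 / 0.65 = 450.0, against a printed 540. The excess is 540/450 − 1 = 20%, too large for rounding.

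**4. Could another reading give 540?** None of those tried does.

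| Reading | Enrolled |
|---|---|
| Multiply 292.5 by 1.35 instead of dividing by 0.65 | 395 |
| 43 events with exponential event accrual (318.5 ATP subjects) | 490 |
| 14% taken as an annual probability (301.5 ATP subjects) | 464 |
| Freedman's formula (49 events), linear person-time | 513 |
| Freedman's formula, exponential accrual | 558 |

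One-sided tests need fewer events (35 by Schoenfeld, 40 by Freedman) and so fewer subjects. The Freedman readings also contradict the stated 43 events, and exponential accrual contradicts the stated 292.5.

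**5. What 540 yields on the printed inputs.** The method is the one that reproduces steps 1 and 2.

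| Enrolled | ATP subjects (×0.65) | Expected events (×1.5×0.098) | Power |
|---|---|---|---|
| 450 | 292.5 | 43.0 | 85.2% |
| 532 | 345.8 | 50.8 | 90.4% |
| 540 | 351.0 | 51.6 | 90.8% |
| 548 | 356.2 | 52.4 | 91.2% |

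The rows for 532 and 548 cover the 540±8 in the Protocol Summary.

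**6. What would make 540 correspond to 43 events and 85%.** Changing one input at a time:

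- Retention at the stated rates: 292.5/540 = 54.2%.
- Control rate at 65% retention and hazard ratio 0.4: 43 / (351 × 1.5 × 0.7) = 0.1167, or about 11.7 per 100 person-years. The factor 0.7 is (1 + 0.4)/2.

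**7. Related figures.** The first target, 344, equals 292.5/0.85 = 344.1. That suggests a fixed ATP requirement with retention assumed at 85% at first; the 85% retention is an inference and is not printed. The second interim trigger in Protocol 11.3, about one third of per-protocol subjects with N = 98, matches 292.5/3 = 97.5 and not 351/3 = 117. So 292.5 is still the working base elsewhere in the protocol.

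**The case against.** The best reply is that the documents already say where 540 came from. The paragraph after the faulty sentence attributes it to the DSMB, and SAP 14 says the aim was to maintain 85% power. SAP 14 also says that the 2014 increase was meant to replace dropouts, and SAP 11 reports early discontinuation above what was anticipated. Taken together, 540 reads as compensation for a shortfall, not as a margin. On that reading, printing 91% would advertise power that nobody expected. Both true statements (43 events give 85%; 292.5 ATP subjects give 43 events) survive, and no passage states outright an expected count at 540. Hence, the argument goes, this is one sentence that was not updated, and the point is editorial.

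Much of that is fair:

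- Pairing 540 with 85% in SAP 14 is no contradiction, because the goal is a number of events.
- N = 98 is consistent with the ATP requirement still printed, so it corroborates the 292.5 base and is not a second defect.
- The 91% depends on the method. At 351 ATP subjects, exponential accrual gives 47.4 events and 88%; Freedman at 51.6 events gives 87%. Neither method reproduces the documents' own figures: exponential accrual gives 39.5 events from 292.5 subjects, and Freedman gives 80% power at 43 events.

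What does not stand is that the DSMB paragraph cures the problem. It gives the history of 540, while the derivation still presents the number as computed. The record points towards a shortfall, but no revised input for the 2015 step appears in either document. That missing input is what a reader would need.

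**Conclusion.** The concern holds. The enrollment figure in Protocol 11.2 and SAP 5 does not follow from the inputs beside it: they give 450, and 540 is 20% higher. This conclusion needs only the division and no modelling assumption.

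On the same inputs, 540 enrolled implies about 52 expected events and 91% power. That assumes linear person-time, full 1.5-year follow-up for 65% of those enrolled, and Schoenfeld's formula, all as the documents use them. It is indicative only, because subjects who meet an ATP exclusion are censored at that date (Protocol 11.4.1) and so still contribute some follow-up.

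The 43-event goal, its 85% power, alpha and the analysis are unaffected, and no loss of power is shown. It should still be corrected: the error is certain, it sits in both documents, and it concerns the size of the trial.

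**What to change.** In Protocol 11.2 and SAP 5, state that the formula gives 450 and that 540 is the increase the DSMB recommended in September 2015. Then add one of the following:

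- **If the assumptions did not change:** give the expected yield at 540 under them (about 52 events, about 91% power), labelled as conditional on 65% retention and 14 per 100 person-years.
- **If the 2015 review rested on a revised assumption:** print that assumption with its matching events and power. For 43 events and 85%, this would be, for example, about 54% ATP retention at unchanged rates, or about 11.7 per 100 person-years on control at 65% retention.

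The sponsor and the data coordinating center should establish from the 2015 review which applies; 91% should not be printed if the inputs had in fact been revised. Keep the 43-event goal as it is.

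The cost is a wording change in each document, with no effect on enrollment, event goal, alpha or analysis. Protocol 14.2 requires IRB approval of amendments, so if the protocol is not otherwise being reopened, the correction can be made in SAP 5 and carried into the study report.
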